10.1. Estimand framework

A summary of the attributes of the primary estimand is provided in Table 1.

Table 1. Estimand attributes for the primary efficacy analysis

Estimand attribute	Description of attribute
Target population	All treated population: All patients treated with CDX-3379.
Primary patient-level variable	Best overall response (BOR) according to RECIST 1.1. Patients can have a BOR of complete response (CR), partial response (PR), stable disease (SD), progressive disease (PD), or unknown.
Handling of intercurrent events	Alternative anti-cancer therapies will be intercurrent events in the determination of BOR. Assessments that occur after the date of documented progression per RECIST 1.1. or the date of anti-cancer treatment, whichever occurs first, will not contribute to the determination of BOR.
Population-level summary	ORR, defined as the percentage of patients who achieve a best response of CR or PR, confirmed according to RECIST 1.1., for all patients treated with CDX-3379 in combination with cetuximab.

The trial product estimand is defined as ORR based on assessments on or prior to the date of PD or data of anti-cancer therapy, whichever occurs first. Patients who discontinue study therapy for reasons other than progression will continue to have tumor assessments until disease progression or initiation of subsequent anti-cancer therapy, whichever occurs first. Therefore, treatment discontinuation is not considered an intercurrent event. The primary efficacy analysis will be an estimation analysis for this estimand (point estimate of ORR and associated 95% confidence interval).

Duration of response is an important secondary analysis because it characterizes ORR. A summary of the attributes of the estimand associated with this important secondary endpoint is provided in Table 2.

Table 2. Estimand attributes for the important secondary efficacy analysis

Estimand attribute	Description of attribute
Target population	All patients treated with CDX-3379 who have a BOR of confirmed CR or PR (objective response).
Primary patient-level variable	Duration of response is calculated as the date of first CR or PR that is subsequently confirmed to date of documented disease progression or death due to any cause, whichever occurs first. In patients who have objective response and are progression-free and alive at the time of the analysis, duration of response is calculated as the date of first CR or PR that is subsequently confirmed to the date of last evaluable tumor assessment.
Handling of intercurrent events	Alternative anti-cancer therapies may be intercurrent events in the calculation of duration of response. In patients with objective response who receive an anti-cancer therapy prior to documented disease progression, duration of response will be censored on the start date of the anti-cancer therapy.
Population-level summary	A Kaplan-Meier plot will show duration of response in patients who have objective response. The median duration of response will be shown as a population-level summary statistic.

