Endpoints:	
Primary Endpoint:
 
• ORR: The percentage of patients who achieve a CR or PR, confirmed according to RECIST 1.1. Best response is recorded between the date of first dose and the date of documented progression per RECIST 1.1 or the date of subsequent anti-cancer treatment, whichever occurs first. For patients without documented progression or subsequent anti-cancer treatment, all available tumor assessments will contribute to the best response assessment. 
Secondary Endpoints:
 
• CBR: The percentage of patients who achieve best response of confirmed CR or PR, or stable disease (SD) for at least 12 weeks. Best response is assessed as described for ORR.• DOR: The interval from which measurement criteria are first met for CR or PR until the first date that progressive disease is objectively documented or death, whichever occurs first. Patients who have not progressed or died will be censored on the date of last evaluable tumor assessment; patients who did not have any on-study assessments and have not died will be censored on the date of first dose. If a patient receives subsequent anti-cancer treatment before documented progression, then DOR will be censored on the last evaluable tumor assessment on or before the start date of subsequent anti-cancer treatment.• PFS: The time from start of CDX-3379 to time of progression or death, whichever occurs first. Patients who have not progressed or died will be censored on the date of last evaluable tumor assessment; patients who did not have any on-study assessments and have not died will be censored on the date of first dose. If a patient receives subsequent anti-cancer treatment before documented progression, then PFS will be censored on the last evaluable tumor assessment on or before the start date of subsequent anti-cancer treatment.• OS: The time from start of CDX-3379 to death. Patients who have not died will be censored on the date of last contact.• Safety: Safety will be assessed by vital sign measurements, clinical laboratory tests, physical exams, ECGs, and the incidence and severity of adverse events (graded according to National Cancer Institute Common Toxicity Criteria for Adverse Events (NCI CTCAE v 5.0.)).• Pharmacokinetics: Noncompartmental PK parameters will be determined using CDX-3379 serum concentration data obtained prior to, at completion of, and one hour after each CDX-3379 administration, as well as on days 8 and 15 of the first cycle, and 30 days post-treatment.• Immunogenicity: Patients will be monitored for the development of anti-drug antibodies (ADA) to CDX-3379. Samples will be collected for future evaluation of the neutralizing capacity of ADA.

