16. To be collected at 30-day follow-up visit, only if additional anticancer therapy has not been started.
17. Biomarker blood samples to be collected predose at Cycle 2, 3, 5, 7, and 9.

Continued (page 2 of 3)

Exhibit 4. Schedule of assessments, continued

	Screening	Treatment Period				End of Treatment (EOT) ²	Follow-up Period ³		
		Cycle 1		Cycle 2 and subsequent cycles					
		Day 1	Day 8	Day 15	Day 1		30-day	Survival follow-up	
Visit Window ¹	Day -28 to -1		± 1 day	± 1 day			± 3 days	Every 12 weeks ± 2 weeks until study closure	
Diagnostic imaging/ response assessment ¹⁸	×				× ¹⁸	× ¹⁸		× ¹⁸	
Administer CDX-3379 ¹⁹		×			×				
Administer cetuximab ²⁰		×	×	×	×				
Concomitant medication review ²¹	×	×	×	×	×	×	×	×	
Adverse event monitoring ²²		×	×	×	×	×	×	×	
Survival follow-up								×	
18. Disease evaluation done at screening, near the end of every 2nd cycle (i.e., after day 15 of Cycles 2, 4, 6, 8, etc. and prior to dosing for the next cycle), and, for patients who have not experienced progression at end of treatment, every 12 (±2) weeks until progression or initiation of alternate cancer therapies. Disease evaluation is required at end of treatment only if disease progression is not previously documented. If a partial or complete response is noted, a follow-up radiographic assessment must be done no sooner than 28 days later to confirm response. Prior to any intervention (such as surgical resection, palliative radiation or alternate anticancer therapy), every effort should be made to perform a tumor response assessment in order to document progression and/or confirm an objective response.									
19. Unless otherwise specified, all study assessments should be performed prior to administration of study treatment and may be performed up to 24 hours prior to treatment administration if assessments remain within the specified visit window. CDX-3379 should be administered first, with a 1-hour observation period before administration of cetuximab.									
20. Cetuximab will be administered weekly on Days 1, 8, and 15 of each cycle. On Day 1 of each Cycle, cetuximab should be administered approximately 1 hour after the completion of CDX-3379 administration and after collection of the 60 minute post-infusion PK blood sample. As a routine precaution, patients should be observed for at least 1 hour after the end of the cetuximab infusion.									

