4.10. Censoring

Censoring methods for the primary and secondary efficacy endpoints are outlined in Section 6.

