5.6. Prior anti-cancer therapies

The number and percentage of patients who underwent prior cancer-related surgery, radiation, and systemic therapies will be summarized. Prior systemic therapy regimens will be categorized and presented by WHO Drug Preferred Name and summarized as:

- The number and percentage of prior systemic cancer therapy regimens (1, 2, 3, 4, 5 or more),
- The number and percentage of prior systemic cancer therapy regimens in the advanced/metastatic setting, and
- Types of prior systemic cancer therapies of interest, as categorized by medical review.

The best response (CR, PR, stable disease [SD], progressive disease [PD], or unknown) to the most recent prior regimen will be presented in addition to the reason for discontinuing.

6. Efficacy analyses

To support calculation of ORR, CBR, DOR, and PFS, tumor assessments will be performed approximately every six weeks during treatment. Patients who discontinue treatment in the absence of progression will continue to have assessments approximately every 12 weeks until documented progression or initiation of alternate anti-cancer therapies. The investigator will assess tumor response in accordance with RECIST 1.1 guidelines [2] (see Section 10.3). The investigator will record the overall response at each timepoint (CR, PR, SD, PD, or NE) as well as the date of first response (CR or PR) and date of PD. Best overall response (BOR) will be derived from timepoint responses per RECIST 1.1 guidelines.

The efficacy analyses will be conducted within the estimand framework. The details are provided in Appendix 10.1.

The primary analysis is planned upon achievement of complete data for ORR, i.e., after all treated patients have been followed for at least six months after receiving their first dose of study treatment or after all patients have discontinued study treatment, whichever occurs sooner.

Following the primary analysis, study follow-up will continue until adequate data are available to support secondary analyses.

The primary efficacy analysis will be based on the all treated population. Additional supportive efficacy analyses will be performed using the FAT1 mutation-positive treated patients, FAT1 or NOTCH mutation-positive treated patients, and all treated patients with a primary tumor site of oral cavity. A patient is considered NOTCH mutation-positive if they express a mutation in any one of the NOTCH family genes (NOTCH1, NOTCH2, or NOTCH3).

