6.2. Secondary efficacy endpoints

6.2.1. Duration of response

DOR is defined as the interval from which measurement criteria are first met for CR or PR until the first date that progressive disease is objectively documented or death, whichever occurs first. Patients who have not progressed or died will be censored on the date of last evaluable tumor assessment; patients who did not have any on-study assessments and have not died will be censored on the date of first dose. If a patient receives subsequent anti-cancer treatment before documented progression, then DOR will be censored on the last evaluable tumor assessment on or before initiation of subsequent anti-cancer treatment. The censoring rules are outlined in Exhibit 6.

DOR will be estimated in the all treated population using the Kaplan-Meier (KM) product limit method and displayed graphically. The KM estimate of the median DOR and the corresponding two-sided 95% CI, calculated using the Brookmeyer and Crowley's method (log-log transformation), will be presented.

Time to response, defined as the time from first dose date to the date of first confirmed response (CR or PR), will also be estimated in the all treated population using the Kaplan-Meier (KM) product limit method. The KM estimate of the median time to response and the corresponding two-sided 95% CI, calculated using the Brookmeyer and Crowley's method (log-log transformation), will be presented alongside DOR.

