6.2.4. Progression-free survival

PFS is defined as the time from the start of study treatment to the time of progression or death, whichever occurs first. Patients who have not progressed or died will be censored on the date of last evaluable tumor assessment; patients who did not have any on-study assessments and did not die will be censored on the date of first dose. If a patient receives subsequent anti-cancer treatment before documented progression, then PFS will be censored on the last evaluable tumor assessment on or before initiation of subsequent anti-cancer treatment. The censoring rules are outlined in Exhibit 6.

Exhibit 6. Censoring rules

Situation	Date of Event or Censoring	Outcome
Progression	Date of progression	Event
Death without progression	Date of death	Event
No baseline disease assessment	Date of first dose	Censored
No on-study disease assessments and no death	Date of first dose	Censored
No progression and no death	Date of last evaluable tumor assessment	Censored
Subsequent anti-cancer therapy before documented progression	Date of last evaluable tumor assessment on or before initiation of subsequent anti-cancer therapy	Censored

PFS will be estimated in the all treated population using the KM product limit method and displayed graphically. The KM estimate of the median PFS and the corresponding two-sided 95% CI, calculated using the Brookmeyer and Crowley's method (log-log transformation), will be presented.

The number and percentage of patients with an event and the type of event (progression or death) will be summarized. The status of patients who are censored in the PFS KM analysis will be presented using the following categories:

- No baseline or inadequate baseline assessment
- No post-baseline or death before first scheduled assessment
- Received additional anti-cancer therapy
- Death or progression after ≥ 2 missed assessments
- Alive and without disease progression

The KM estimates of the median PFS rate at 3 months and 6 months will be presented with the corresponding 95% CIs.

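### SAP Appendix 10.1 Table 2 censors duration of response at the start of new anti-cancer therapy, whereas SAP 6.2.1, Exhibit 6 and the protocol censor at the last evaluable scan on or before it

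*SAP*

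**What the plan says.** SAP Appendix 10.1 Table 2 sets out the DOR estimand. Its row on intercurrent events covers a responder who gets anti-cancer therapy before documented progression: "duration of response will be censored on the start date of the anti-cancer therapy".

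Four other places give a different date for the same patient:

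- SAP 6.2.1: "DOR will be censored on the last evaluable tumor assessment on or before initiation of subsequent anti-cancer treatment". The section then names Exhibit 6 as the place for the rules, so Exhibit 6 covers DOR as well as progression-free survival (PFS).
- SAP Exhibit 6 (in 6.2.4), row on subsequent therapy: "Date of last evaluable tumor assessment on or before initiation of subsequent anti-cancer therapy".
- Protocol synopsis (Endpoints) and Protocol 12.2, in the same words: "DOR will be censored on the last evaluable tumor assessment on or before the start date of subsequent anti-cancer treatment".

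Three statements bear on which rule governs. SAP 4.10 says: "Censoring methods for the primary and secondary efficacy endpoints are outlined in Section 6". The opening of SAP Section 6 says: "The efficacy analyses will be conducted within the estimand framework. The details are provided in Appendix 10.1". SAP Section 1 puts the SAP above the protocol where they differ, but does not rank one part of the SAP above another.

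On the weight of the endpoint, Appendix 10.1 says: "Duration of response is an important secondary analysis because it characterizes ORR".

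**The concern.** Two dates are prescribed for one event in one endpoint. A programmer who works from Table 2 is following the SAP, and so is one who works from 6.2.1.

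The Table 2 date credits a responder with response time between the last scan and the start of the next therapy, although no scan shows that the response lasted that long. Table 2 is also uneven within itself: a responder who is alive and progression-free at the analysis stops at the last evaluable assessment, while one who moves to another therapy is carried past it. The endpoint affected is the one the SAP uses to characterize the primary result, and it may rest on few responders.

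**Working it through.** The documents give no figure that depends on this rule, so there is none to reproduce. The check covers the direction of the difference, the size of the gap, and its effect on the planned summary, which is the Kaplan-Meier (KM) plot and median.

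**Direction.** The KM estimate is S(t) = Π(1 − d/n) over the event times up to t, where d is the number of events and n the number at risk. The affected patients are censored under both rules, so the event times and every d are the same. The later Table 2 date can only keep a patient in n for longer. Each factor is therefore equal or larger, and the curve is equal or higher. This needs no assumption about the data.

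**Gap for one patient.** Gap = start of new therapy − last evaluable scan. Inputs: scans about every 6 weeks on treatment and every 12±2 weeks after stopping without progression (SAP Section 6; Exhibit 4 notes 3 and 18), and 30.4375 days per month (SAP 4.4). If no scan is missed, the approximate maximum is:

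| Schedule | Days | Months |
|---|---|---|
| 6 weeks | 42 | 42/30.4375 = 1.38 |
| 12 weeks | 84 | 84/30.4375 = 2.76 |
| 12+2 weeks | 98 | 98/30.4375 = 3.22 |

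If therapy starts are spread evenly between scans (an assumption), the average is about half the interval, or about 3 weeks on the 6-week schedule. The gap is longer if a scan is missed or not evaluable. It is shorter if Exhibit 4 note 18 is followed, which asks that before alternate therapy "every effort should be made to perform a tumor response assessment in order to document progression and/or confirm an objective response".

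**Effect on the median.** Both examples use five responders with assumed times in weeks from response. The median is the first time at which S is 0.5 or less. No S value below equals 0.5, so the convention for that case does not matter here.

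*Example A, one patient on new therapy.* Progression at weeks 12, 18, 24 and 36; the fifth patient has the last scan at week 13.

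| Censoring date | S(12) | S(18) | S(24) | S(36) | Median |
|---|---|---|---|---|---|
| Week 13 (6.2.1) | 0.800 | 0.533 | 0.267 | 0 | 24 |
| Week 19 (Table 2, 6-week gap) | 0.800 | 0.600 | 0.300 | 0 | 24 |
| Week 25 (Table 2, 12-week gap) | 0.800 | 0.600 | 0.400 | 0 | 24 |

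The curve rises but the median stays the same.

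*Example B, two patients on new therapy.* Progression at weeks 12, 24 and 36; two patients have the last scan at week 19 and new therapy at week 25, a full 6-week gap.

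| Week | 6.2.1 (censored at 19) | Table 2 (censored at 25) |
|---|---|---|
| 12 | 1 − 1/5 = 0.800 | 1 − 1/5 = 0.800 |
| 24 | 0.800 × (1 − 1/2) = 0.400 | 0.800 × (1 − 1/4) = 0.600 |
| 36 | 0 | 0 |
| Median | 24 | 36 |

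If both patients instead had a note 18 scan at week 24.5, 6.2.1 would also have four at risk at week 24. Then S(24) = 0.600 and both rules give a median of 36.

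**The case against.** The strongest reply is that the SAP already settles the matter. Section 4.10 assigns censoring to Section 6, 6.2.1 states the scan-based rule, and Exhibit 6 repeats it, so Table 2 is one stale cell in an appendix. Much of this stands: Section 6 is the better-supported rule. But Section 6 itself sends the reader to Appendix 10.1 for details, and a cell that states a contrary rule should be corrected.

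It is also fair that disagreement with the protocol is no fault in itself. The SAP prevails over the protocol, and Protocol Section 12 lets the SAP modify its plans, requiring an amendment only for major changes to the primary endpoint or its analysis. The fault is the conflict inside the SAP.

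Three stronger readings are tempting, and the documents do not support them:

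- *That the dates typically differ by a whole scan interval.* That is roughly the maximum with scans on schedule, and a scan before new therapy shrinks the gap.
- *That the reported median will be inflated, or inflated with a known frequency.* The documents give no rate of new therapy before progression, so any frequency rests on an assumed rate. It also depends on how the median is defined when S equals exactly 0.5. In one simulation setting (4 responders, 25% assigned new therapy, 6-weekly scans), the median differed in 0.6% of runs when taken as the first time S is 0.5 or less, and in 3.0% with the midpoint rule.
- *That the SAP censors some PFS events.* The 6.2.4 list of statuses for censored patients has a category for progression or death after at least two missed assessments, and another that mentions death before the first scheduled assessment. But 6.2.4 names Exhibit 6 as the rule, and Exhibit 6 counts progression and death without progression as events. Under it the first category is empty. The second can be read as neither an assessment nor a death, which agrees with Exhibit 6. No PFS estimate changes.

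**Conclusion.** The DOR conflict is real and minor. The Table 2 cell is wrong as written because it contradicts SAP 6.2.1, Exhibit 6 and the protocol. The direction is certain: with the same events, the Table 2 rule leaves the DOR curve unchanged or raises it. The size is modest, with a gap for each affected patient of up to about one scan interval and about half of that on average, assuming scans on schedule and therapy starts spread evenly between them. Only responders who start new therapy before progression are affected. The median often stays put, but with few responders it can move, as in the assumed 24 against 36 weeks. ORR, sample size and power are unaffected, and no formal testing is planned.

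The population wording for DOR (all treated patients in 6.2.1, confirmed responders in Table 2) is a label mismatch only, since a non-responder has no start date for DOR.

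**What to change.** In Table 2, replace the censoring date with the 6.2.1 rule: the last evaluable tumor assessment on or before initiation of new anti-cancer therapy.

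The following are wording notes with no effect on estimates:

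- In 6.2.1, say that DOR is estimated in confirmed responders, and drop the clause on patients without on-study assessments, which cannot apply to them.
- In the 6.2.4 list of censored patients, remove the category for progression or death after two or more missed assessments.
- In the same list, reword the early-death category as no post-baseline assessment and no death.

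The cost is a revision of SAP text before database lock, which SAP 4.11 provides for. No new data or analyses are needed.

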10.2. ECOG Performance Status

Exhibit 9. ECOG Performance Status

Grade	ECOG
0	Fully active, able to carry on all pre-disease performance without restriction
1	Restricted in physically strenuous activity but ambulatory and able to carry out work of a light or sedentary nature, e.g., light house work, office work
2	Ambulatory and capable of all selfcare but unable to carry out any work activities. Up and about more than 50% of waking hours.
3	Capable of only limited selfcare, confined to bed or chair more than 50% of waking hours.
4	Completely disabled. Cannot carry on any selfcare. Totally confined to bed or chair.
5	Dead

As published in Am. J. Clin. Oncol [5]

10.3. RECIST 1.1 criteria

To assess objective response or future progression, it is necessary to estimate the overall tumor burden at baseline and use this as a comparator for subsequent measurements. All baseline evaluations should be performed as close as possible to the treatment start and never more than four weeks before the beginning of the treatment. The same method of assessment and the same technique should be used to characterize each identified and reported lesion at baseline and during follow-up. Imaging based evaluation should always be done rather than clinical examination, unless the lesion(s) being followed cannot be imaged but are assessable by clinical exam. (See “Methods of Lesion Measurement” for further guidance.)

At baseline, lesions should be identified as either “Target” or “Non-Target” as follows:

Target Lesions:

- Up to a maximum of five measurable target lesions total (with a maximum of two target lesions per organ) should be identified as target lesions and will be recorded and measured at baseline. (This means in instances where patients have only one or two organ sites involved a maximum of two and four lesions respectively will be recorded.)

- Target lesions should be selected on the basis of their size (lesions with the longest diameter), be representative of all involved organs, and should be those that lend themselves to reproducible repeated measurements. It may be the case that, on occasion, the largest lesion does not lend itself to reproducible measurement in which circumstance the next largest lesion which can be measured reproducibly should be selected.
- All target lesion measurements should be recorded in metric notation, using calipers if clinically assessed.
- A sum of the diameters (longest for non-nodal lesions, short axis for nodal lesions) for all target lesions will be calculated and reported as the baseline sum diameters. The baseline sum diameters will be used as reference to further characterize any objective tumor regression in the measurable dimension of the disease. (See "Tumor response evaluation".)

Non-Target Lesions:

- All other measurable/non-measurable lesions (or sites of disease) including pathological lymph nodes should be identified as non-target lesions and should also be recorded at baseline. It is acceptable to record multiple non-target lesions involving the same organ as a single item on the case report form (e.g. 'multiple enlarged pelvic lymph nodes' or 'multiple liver metastases').
- Non-target lesions should be followed as 'present', 'absent', or in rare cases 'unequivocal progression'. (See "Tumor response evaluation".) While some non-target lesions may actually be measurable, they need not be measured and instead should be assessed only qualitatively.

